4.4. Background therapy

All patients enrolled in the study will receive background therapy according to standard clinical practice (including antimicrobial, prophylactic, and best supportive care therapies as deemed appropriate by the Investigator), excluding investigational drugs. Analgesic treatment, transfusion of blood products, electrolyte and glucose infusions, IV parenteral nutrition, inotropic support, antibiotics, anti-fungal and anti-viral treatments, ultrafiltration or hemodialysis, as well as general supportive care are permitted.

4.5. Concomitant and prohibited therapy

Patients previously treated with tocilizumab can be enrolled in the study, if considered not benefitting from the treatment, in the opinion of the Investigator.

Concomitant use of IL-1 inhibitors (e.g., anakira, canakinumab), TNF inhibitors, JAK inhibitors, and chloroquine/hydroxychloroquine is not allowed. If any of these therapies are initiated at the discretion of the Investigator (e.g., as rescue therapy due to worsening of the patient's condition), then the patient should be withdrawn from study.

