3.3. Secondary endpoints

3.3.1. PaO_2/FiO_2 ratio as categorical variable: mild 200 mmHg < $PaO_2/FiO_2 \le 300$ mmHg; moderate 100 mmHg < $PaO_2/FiO_2 \le 200$ mmHg; severe $PaO_2/FiO_2 \le 100$ mmHg.

- 3.3.2. For patients already on mechanical ventilator at time of randomization, the number of days on ventilator after randomization.
- 3.3.3. For patients not on mechanical ventilator at time of randomization, the number of days not requiring invasive mechanical ventilation (i.e., ventilator-free days).
- 3.3.4. PaO_2/FiO_2 ratio as continuous variable.
- 3.3.5. Resting SpO₂ adjusted by FiO₂.
- 3.3.6. Change in oxygen supplementation requirements.
- 3.3.7. Quantitative and qualitative assessment of pulmonary lesions by chest HRCT scans at baseline and at day 14 and week 12.
- 3.3.8. Time to hospital discharge.
- 3.3.9. Time to all-cause mortality up to 28 days.
- 3.3.10. Proportion of patients discharged from ICU and alive within 28 days.
- 3.3.11. Proportion of patients alive within 28 days.

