4. STUDY DESIGN AND METHODS

4.1. Study design

This is a randomized, open-label, parallel-arm study to investigate the efficacy and safety of pamrevlumab in patients with documented SARS-CoV-2 infection. The study consists of screening, a treatment period, and a follow-up period.

The study will enroll patients who have been hospitalized and who are not currently on invasive mechanical ventilation. The treatment period is open ended, and patients will be randomized to treatment with pamrevlumab or standard of care in a 1:1 ratio according to a pre-generated randomization list. Pamrevlumab dosing, 30 mg/kg IV, will be administered at day 1, day 7 and day 14. Day 1 is defined as the day of randomization which must also include administration of the first dose of pamrevlumab for patients in the active treatment arm.

Based on Investigator's decision, treatment may be continued every 3 weeks after day 14, up to 11 weeks.

Since the treatment scheme of pamrevlumab for this study is more intense as compared to previous studies conducted in IPF patients, as a further safety measure the first 3 patients randomized to receive the experimental drug will be treated one at a time, leaving a 1-week observation period between them.

A follow-up by visit or phone call will be performed 8 and 12 weeks after the end of the last dose of treatment. The treatment period for an individual patient will not exceed 11 weeks. The end of the study is defined as last patient last follow-up visit/phone call.

The study design has a total sample size of approximately 68 patients and consists of two stages. At the end of Stage 1 (Stage 1 requires 23 patients on pamrevlumab treatment arm), analyses of efficacy and safety will take place with a potential to stop the study for futility or for efficacy. A data

review committee composed of experts in respiratory medicine and intensive care will be involved in study oversight and interpretation of the study results. In patients showing worsening of clinical condition, independently of the treatment arm, the Investigator is free to introduce any therapy considered necessary.

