4.7. Statistical methods

For futility testing in Stage 1, a responder rate definition will be used. Patients randomized to receive pamrevlumab are considered responders if the total number of days on ventilation is \leq 15 days after the first dose of pamrevlumab. In addition, chest HRCT scans obtained at enrollment and day 14 \pm 2 will used as supportive analyses in the assessment of futility.

Analysis of continuous endpoints will be conducted using analysis of covariance (ANCOVA) model with baseline value as a covariate and relevant baseline prognostic factors as other covariates.

Analysis of categorical endpoints will be conducted using either Fishers Exact test or Cochran-Mantel-Haenszel test comparing the categories between the two treatment arms.

Analysis of the time to mechanical ventilation, time to all-cause mortality, and time to hospital discharge, respectively, will be undertaken by plotting Kaplan-Meier curves. Hazard ratios will be estimated using the Cox proportional hazards model and these will be presented together with 95% two-sided confidence intervals. Other statistical methods will be applied, as appropriate.

5. Subject withdrawal criteria

Subjects may withdraw from the study at any time, for any reason. Reasons for discontinuing study drug treatment, as well as reasons for withdrawing from study, will be captured on CRF.

Reasons for withdrawing the subject from the study may include the following:

- 5.1. Any safety concern in the Investigator's opinion, that precludes further study participation
- 5.2. Pregnancy
- 5.3. Withdrawal of Consent

6. Pamrevlumab: storage, preparation and use

Pamrevlumab is a fully human IgG1 kappa monoclonal antibody that binds to CTGF and is formulated as solution for administration by IV infusion.

Pamrevlumab is supplied in single-use glass vials containing sterile, preservative-free solution 10 mg/ml pamrevlumab. The solution is composed of 10 mg/mL pamrevlumab, 1.60 mg/mL L-histidine, 3.08 mg/mL L-histidine HCl, 8.01 mg/mL sodium chloride, and 0.05 mg/mL polysorbate 20, resulting in a solution with a tonicity of approximately 290 mmol/kg and a pH of 6.0.

Vials of pamrevlumab must be stored refrigerated (2°C to 8°C), in a temperature- controlled and monitored environment, protected from light, and in a securely locked area to which access is limited to appropriate study personnel. Documentation of the storage conditions must be maintained.

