9. SCHEDULE OF EVENTS

ASSESSMENTS	Screening		Treatment											ONLY If EOT = Day 14 ^{2,4}	ONLY If EOT = Day 14 ^{2,4}	Continued Treatment visits for eligible subjects (CTV)	Follow-up			
	Up to 72 hrs prior to Day 1	Day 1 (ba seli ne)	Day 2	Day 3	Day 4	Day 5	Day 6	Day 7	Day 8	Day 9	Day 10	Day 11	Day 12	Day 13	Day 14 ⁴	Day 21 (+/- 2 days)	Day 28 (+/- 4 days)	Dosing Q 3 wks +/- 2 days: Week 5, 8,	Week 12 for all subjects	4 weeks (+/- 7 Days) after last Pamrevlu mab dose
Informed consent	Х																			
Eligibility criteria	Х																			
Medical History	Х																			
Demographic information	Х																			
Physical examination	Х																			
Vital signs ³	Х	X1	Х	Х	Х	Х	Х	X ¹	Х	Х	Х	Х	Х	Х	X ¹			X ¹		
ECG	Х																			
Chest HRCT	Х														Х				Х	
Laboratory assessments (local)	Х	Х	Х	Х	Х	Х	Х	Х	Х	Х	Х	Х	Х	Х	Х			Х		
Blood samples for Immunogenicity Assessments		Х						Х							Х					Х
Urine pregnancy test ⁶	Х																			
Randomization		Х																		
Concomitant medications	Х	Х	Х	Х	Х	Х	Х	Х	Х	Х	Х	Х	Х	Х	Χ	Х	Х	X	Х	Х
Infusion		Х						Х							Х					
Arterial Blood Gases (ABG) ³	Х	Х	Х	Х	Х	Х	Х	Х	Х	Х	Х	Х	Х	Х	Х					
PaO ₂ /FiO ₂ ³	Х	Х	Х	Х	Х	Х	Х	Х	Х	Х	Х	Х	Х	Х	Χ					
Resting SpO ₂ (3 times/day) ³	Х	Х	Х	Х	Х	Х	Х	Х	Х	Х	Х	Х	Х	Х	Х					
Oxygen supplementation Needs ^{3, 5}	Х	Х	Х	Х	Х	Х	Х	Х	Х	Х	Х	Х	Х	Х	Х					
Adverse events	Х	Х	Х	Х	Х	Х	Х	Х	Х	Х	Х	Х	Х	Х	Х	Х	Х	Х	Х	Х
Survival and Hospital Discharge Status																Х	Х		Х	Х

¹On infusion days, vitals taken within 30 minutes prior and 30 min after infusion; otherwise vitals taken daily ²Follow-up visits to be done in person or by phone ³Only measured until subject is discharged from the ICU/CCU. ⁴Subjects ending treatment on Day 14 should be contact by phone or return for a visit on Days 21 and 28 for a vital status check. ⁵Including need for mechanical ventilation including ventilator settings, or supplemental oxygen including mode of oxygen delivery ⁵Only for women of childbearing potential or last menstruation <1 year.

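### Section 4.5 takes patients who start a listed drug out of the study, not just off pamrevlumab, and no text clearly keeps them in follow-up to Day 28

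*Protocol*

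**What the plan says.** Protocol Section 4.5 bars concomitant IL-1, TNF and JAK inhibitors and chloroquine or hydroxychloroquine. If one is started, and the protocol's own example is "as rescue therapy due to worsening of the patient's condition", "then the patient should be withdrawn from study". The rule is not limited to the pamrevlumab arm.

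Section 5 keeps two events apart: "Reasons for discontinuing study drug treatment, as well as reasons for withdrawing from study, will be captured on CRF". 

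The endpoints exposed are in Section 3.3: time to hospital discharge (3.3.8), "Time to all-cause mortality up to 28 days" (3.3.9), discharged from ICU and alive within 28 days (3.3.10) and alive within 28 days (3.3.11). Section 4.7 plans Kaplan-Meier curves and Cox models for these: "Analysis of the time to mechanical ventilation, time to all-cause mortality, and time to hospital discharge".

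Follow-up is described in several places:

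- Section 9, footnote 4: Day 21 and Day 28 vital status contacts for subjects whose treatment ends on Day 14.
- Section 9, a column headed "Week 12 for all subjects", with survival and discharge status marked.
- Section 9, a visit "4 weeks (+/- 7 Days) after last" pamrevlumab dose, also with survival and discharge status marked.
- Section 4.1: "A follow-up by visit or phone call will be performed 8 and 12 weeks after the end of the last dose of treatment".

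None of these mentions patients withdrawn under Section 4.5.

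**The concern.** Patients who need rescue are doing worse than the rest. A rule that takes them out of the study, if sites follow it in the usual sense, stops outcome collection in the patients most likely to be ventilated, to stay in hospital or to die. If they are then censored at withdrawal, censoring depends on prognosis, and Kaplan-Meier and Cox estimates are biased. Because the trial is open-label, the decision to give rescue may also differ by arm, so the bias need not cancel.

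The effect falls mainly on mortality and discharge. For the 15-day responder endpoint, an analysis plan can count rescue as non-response, although ventilation data not yet collected are exposed there too. For death and discharge no analysis rule can replace the missing facts. The protocol decides who is followed, so this cannot be left to the SAP.

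**Working it through.** **Step 1. Can the rule mean stopping drug only?** No, for three reasons.

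- Section 5 names drug discontinuation and study withdrawal as distinct events.
- Section 6 shows how the protocol words the milder action: after a hypersensitivity or anaphylactic reaction the patient comes off treatment and is followed for safety for up to 4 weeks. Section 4.5 has no such clause.
- The rule also reaches standard-of-care patients, who have no study drug to stop.

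**Step 2. Does any visit secure Day 28 status?** Take a patient withdrawn after the Day 1 or Day 7 dose.

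| Contact | Covers this patient? |
|---|---|
| Day 21 and Day 28 (footnote 4) | Not named; written for treatment ending on Day 14 |
| 4 weeks ± 7 days after last pamrevlumab dose | No stated date for standard of care; for pamrevlumab see below |
| 8 and 12 weeks after last dose (Section 4.1) | Timed from last dose; withdrawn patients not mentioned |
| Week 12 column | Headed for all subjects; does not say whether this includes the withdrawn |

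The 4-week window is last-dose day + 28 ± 7:

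- last dose Day 1: Day 22 to 36, so it may precede Day 28
- last dose Day 7: Day 28 to 42
- last dose Day 14: Day 35 to 49

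**Step 3. Uncertainty from missing patients.** The protocol gives no rescue or withdrawal rate, so there is no stated figure to reproduce. Arm size is 34 (about 68 patients, 1:1). With k of 34 unknown, the best-to-worst range of an arm's proportion is k/34.

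- k = 2: 2/34 = 5.9 points.
- Two lost in each arm: 4/34 = 11.8 points for the between-arm difference.

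**Step 4. Kaplan-Meier bias.** Let m be true 28-day mortality, c the share of eventual deaths and s the share of survivors who are censored, all before the first death. Apparent mortality is then

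m(1 − c) / [m(1 − c) + (1 − m)(1 − s)].

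Assume m = 0.25 in both arms, with c = 0.10 in one and 0.30 in the other. All of these are assumptions.

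| Survivors leave at | c = 0.10 | c = 0.30 | Spurious difference |
|---|---|---|---|
| same rate, s = c | 25.0% | 25.0% | 0 |
| half the rate, s = c/2 | 0.225/0.9375 = 24.0% | 0.175/0.8125 = 21.5% | 2.5 points |
| not at all, s = 0 | 0.225/0.975 = 23.1% | 0.175/0.925 = 18.9% | 4.2 points |

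At s = c/2 the difference is 1.6 points for m = 0.15 and 3.1 points for m = 0.35.

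Placing withdrawals early is a simplification. At the other end, with no survivor leaving and each withdrawal just before death, apparent survival is (1 − m)^(1 − c). Mortality is then 1 − 0.75^0.9 = 22.8% against 1 − 0.75^0.7 = 18.2%, a difference of 4.6 points. Timing alone changes little.

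**Step 5. Scale.** The assumed imbalance is (0.30 − 0.10) × 0.25 × 34 = 1.7 patients. The standard error of the difference is √(2 × 0.25 × 0.75/34) = 0.105, or 10.5 points.

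**The case against.** The strongest counter-argument is that the loss is inferred. Section 4.5 does not end data collection, and the Week 12 column, read literally, includes everyone. A Week 12 status check would normally yield a date of death or discharge, from which Day 28 status follows. This stands in part: the data may be lost, not must be. But a site told to withdraw a patient from the study can reasonably stop contacting that patient, and nothing tells it otherwise.

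It can also be said that the Day 21 and 28 gap and the undated standard-of-care visit are general scheduling matters. That is true; patients who continue dosing are not in the Day 21 and 28 columns either. The columns matter here only because they offer no safety net for the withdrawn patient.

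Section 4.1 leaves the investigator free to give any therapy on worsening, in either arm, without mentioning withdrawal. This could be read as softening the rule. Section 4.5 is the more specific text and probably governs, so the two sections pull in different directions.

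Three limits are accepted. The trigger is narrow: only the listed drugs count, and rescue is an example, not the only case. Section 4.7 gives no censoring rule, so informative censoring depends on how an analysis plan treats these patients. Time to ventilation appears only in Section 4.7 and is not a listed secondary endpoint; the listed one is ventilator-free days (3.3.3).

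**Conclusion.** The concern holds. The protocol states a withdrawal rule, separates it from stopping drug, and nowhere clearly keeps the affected patients under observation to Day 28. Following it can lose survival and discharge data, and any remaining ventilation data, in a way related to prognosis.

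Neither the size nor the direction of the effect can be known from the protocol. Under the assumed shares the bias in 28-day mortality is at most about 4 to 5 points, and zero if survivors and eventual deaths leave at the same rate. That is less than half the standard error. The confidence is in the wording; the consequence depends on site practice and on how often listed drugs are used. The change is worth making because the loss could not be repaired afterwards and is cheap to prevent.

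**What to change.** Replace the withdrawal sentence in Section 4.5 with wording such as:

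> A patient who starts a listed therapy stops pamrevlumab, if assigned, but stays in the study. Unless consent is withdrawn, all scheduled assessments continue, including ventilation status as scheduled for other patients and survival and discharge status at Days 21 and 28.

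Extend footnote 4 of the Section 9 schedule so that the Day 21 and 28 contacts apply to anyone in either arm who stops early. A cross-reference from the free-choice-of-therapy sentence in Section 4.1 to the revised 4.5 would remove the tension between them.

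The cost is protocol wording and a few chart or phone checks. Sample size does not change.

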4.6. Determination of sample size

This study's sample size is based on Simon's two-stage design (Simon, 1989) on the pamrevlumab arm. For futility testing of Stage 1 of the study, a responder rate definition will be evaluated. Patients randomized to receive pamrevlumab are considered responders if the total number of days on ventilation is \leq 15 days after first dose of pamrevlumab and the patient is alive.

Key assumptions for sample size calculation include the following: (1) type I error rate, α (one-sided): 0.05; (2) power: 90%; (3) response probability of standard of care: 40%; (4) response probability of standard of care + pamrevlumab: 65%.

The null hypothesis that the true response rate is 40% will be tested against a one-sided alternative. In Stage 1, 23 patients will be accrued in pamrevlumab arm. If there are 9 or fewer responses in

these 23 patients, the study may be stopped. Otherwise, 11 additional patients will be accrued for a total of 34 in pamrevlumab treatment group. The null hypothesis will be rejected if 18 or more responses are observed in 34 patients on the pamrevlumab arm. This design yields a type I error rate of 0.05 and power of 90% when the true response rate is 65%.

The study will enroll approximately 50 patients in Stage 1 who will be randomized in 1:1 fashion (pamrevlumab vs. standard of care).

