1. STUDY IDENTIFIERS

1.1. Title of study

An open-label, randomized, parallel-arm study investigating the efficacy and safety of intravenous administration of pamrevlumab versus standard of care in patients with COVID-19.

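### The final efficacy rule tests the pamrevlumab arm against an assumed 40% and leaves out the randomised control; the stated 90% power does not apply to the between-arm comparison, which has about 60–67%

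*Protocol*

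**What the plan says.** The title describes a study of the "efficacy and safety of intravenous administration of pamrevlumab versus standard of care in patients with COVID-19", and section 4.1 randomises 1:1 to pamrevlumab or standard of care, with about 68 patients in total.

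Section 4.6 sizes the study differently: "This study's sample size is based on Simon's two-stage design (Simon, 1989) on the pamrevlumab arm". Its inputs are "type I error rate, α (one-sided): 0.05", 90% power, and response rates of 40% on standard of care and 65% with pamrevlumab added. The hypothesis is "The null hypothesis that the true response rate is 40% will be tested against a one-sided alternative". For the first stage, "In Stage 1, 23 patients will be accrued in pamrevlumab arm". Nine or fewer responders may stop the study; otherwise 11 more pamrevlumab patients are added, and the null is rejected at 18 or more responders out of 34. The section attributes a type I error of 0.05 and 90% power to this rule.

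Section 4.7 then says: "Analysis of categorical endpoints will be conducted using either Fishers Exact test or Cochran-Mantel-Haenszel test comparing the categories between the two treatment arms". The primary endpoint in section 3.1 is a proportion, so it falls within that sentence. No power is given for the comparison. Section 4.1 also allows the study to stop for efficacy, as well as futility, after Stage 1.

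**The concern.** A concurrent randomised control removes the need to know the standard-of-care rate in advance. The rejection rule in section 4.6 brings that need back: it replaces the roughly 34 observed controls with a fixed 40%, for which the protocol gives no source. Any error in the 40% goes straight into the efficacy conclusion. Eighteen responders out of 34 on pamrevlumab would reject the null even if the control arm also had 18 out of 34.

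The protocol also does not say which result decides if the single-arm rule and the between-arm test of section 4.7 disagree. The only power figure it gives belongs to the single-arm design.

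**Working it through.** **Inputs.** From section 4.6: p0 = 0.40, p1 = 0.65, one-sided α = 0.05, Stage 1 n = 23 (continue if more than 9 respond), final n = 34, reject at c = 18 or more. From sections 4.1 and 4.2: 1:1 allocation and about 68 patients, hence 34 per arm. No losses are assumed; losses would lower the between-arm power.

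**Step 1: the plan's own figures.** The exact two-stage success probability at true rate p is

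P(success | p) = Σ over x = 10…23 of Bin(x; 23, p) × P[Bin(11, p) ≥ c − x].

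| Cut-off c | Type I error (p = 0.40) | Power (p = 0.65) |
|---|---|---|
| 18 (printed) | 0.086 | 0.947 |
| 19 | 0.044 | 0.900 |

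A search over two-stage designs for these inputs finds that the minimax design has 23 then 34 patients, continues above 9 and rejects above 18, i.e. at 19 or more. The stated 0.05 and 90% therefore match a cut-off of 19, not the printed 18.

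**Step 2: an inert drug when the assumed 40% is wrong.** The same formula is used, with the true rate p common to both arms. The rates below other than 40% are assumptions chosen to show the range; the protocol gives no figure for the uncertainty.

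| True rate in both arms | P(success), c = 18 | P(success), c = 19 |
|---|---|---|
| 35% | 0.02 | 0.01 |
| 40% | 0.09 | 0.04 |
| 45% | 0.22 | 0.13 |
| 50% | 0.43 | 0.30 |
| 60% | 0.84 | 0.75 |

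Correcting the cut-off lowers these figures but does not remove the dependence on the 40%. The error runs both ways: below 40% the rule works against the drug.

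**Step 3: power of the randomised comparison.** Pooled z-test, n = 34 per arm, difference 0.25, mean rate 0.525:

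- SE under the null = √(2 × 0.525 × 0.475 / 34) = 0.1211
- SE under the alternative = √((0.40 × 0.60 + 0.65 × 0.35) / 34) = 0.1173
- One-sided 0.05: Φ[(0.25 − 1.645 × 0.1211) / 0.1173] = Φ(0.433) = 0.668
- Two-sided 0.05: Φ[(0.25 − 1.960 × 0.1211) / 0.1173] = Φ(0.108) = 0.543

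Fisher's exact test, by enumerating all 35 × 35 outcomes, gives 0.603 (one-sided) and 0.440 (two-sided). Enumerating the pooled z-test in the same way gives 0.695 and 0.529. None of these is near 0.90.

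**Step 4: what 34 per arm can detect.** Against 40%, at one-sided 0.05, a 30-point difference has 81% power by the z-test approximation but 76% by Fisher. Fisher reaches 81% at 32 points. For 90% power at 40% vs 65%, the z-test needs

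[(1.645 × √(2 × 0.525 × 0.475) + 1.282 × √(0.24 + 0.2275)) / 0.25]² ≈ 66.5, i.e. 67 per arm (134 in total).

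**The case against.** The strongest defence is that the single-arm basis is openly declared. Section 4.6 says the Simon design applies to the pamrevlumab arm and ties the 34 patients and the cut-off to that arm. Sizing one arm of a randomised Phase 2 study this way, with a concurrent reference arm, is a known choice. The responder definition limited to pamrevlumab patients is introduced for futility testing, and an unseen SAP could name the primary test. All of this is fair as far as Stage 1 futility goes. It does not cover the rest: section 4.6 also fixes when the null is rejected at the end, and section 4.1 allows stopping for efficacy. A SAP that made the between-arm test decisive would have to contradict the protocol.

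Three stronger readings are tempting and are not supported:

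- *The protocol presents 90% as the power of the randomised comparison.* It does not; it attaches the figure to the pamrevlumab arm. The defect is that no power is given for the comparison that the title promises.
- *The true standard-of-care rate is above 40%, so the rule favours the drug.* The protocol has no data on this. The table in Step 2 is a sensitivity range in both directions, not a forecast.
- *The primary endpoint is undefined for controls.* Section 3.1 words it for patients in general; only the responder definition is limited to one arm. Nor does section 4.7 name the between-arm test as primary. The finding is that the choice is left open while a single-arm rejection rule is fixed.

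**Conclusion.** The point holds and should be corrected before the results are interpreted. As written, the final efficacy conclusion rests on an unsourced 40% and not on the randomised control. A 10-point underestimate of the standard-of-care rate (true rate 50%) gives an inert drug a 43% chance of success under the printed rule, or 30% with a cut-off of 19. Between-arm power at the protocol's own rates is about 60–67% at its one-sided 0.05, and 44–54% if the test is two-sided; section 4.7 does not state which. These figures assume 34 evaluable patients per arm and an unstratified test. The mismatch between the printed cut-off of 18 and the stated 0.05 and 90% adds to the problem, but correcting it alone would not bring the control arm into the decision.

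**What to change.** In sections 4.6 and 4.7:

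1. State that the Simon rule is a Stage 1 futility guide only, and remove the final single-arm rejection rule as the basis for an efficacy claim. If any final cut-off is kept for description, its stated error and power must match it.
2. Name the between-arm comparison in all randomised patients as the primary efficacy test, state its sidedness, and report the risk difference with its confidence interval.
3. Use one responder definition for both arms, counted from randomisation. Section 4.1 makes the day of randomisation the day of the first pamrevlumab dose, so this leaves the starting day in the active arm unchanged.
4. Restate power as about 60–67% at one-sided 0.05 for 40% vs 65%, or give the detectable difference: about 30 points for 80% power by the z-test, about 32 by Fisher.

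A stratified test or covariate adjustment may be useful but is not needed for this correction.

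**Cost.** Wording only, with no extra patients or data. The real price is a clearly lower stated power for the primary test. Restoring 90% for the between-arm comparison would take about 67 per arm instead of 34, which is a separate decision for the sponsor.

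### The final Simon boundary does not give the stated error rate: rejecting at 18 or more of 34 has a type I error of 0.086, not 0.05; 19 or more gives 0.044

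*Protocol*

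**What the plan says.** Protocol section 4.6 (Determination of sample size) fixes the whole design:

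- Method: "This study's sample size is based on Simon's two-stage design (Simon, 1989) on the pamrevlumab arm".
- Error rate: "type I error rate, α (one-sided): 0.05", with power of 90%.
- Hypotheses: "The null hypothesis that the true response rate is 40% will be tested against a one-sided alternative"; the alternative response rate is 65%.
- Stage 1: "In Stage 1, 23 patients will be accrued in pamrevlumab arm". "If there are 9 or fewer responses in" those 23, the study may be stopped; otherwise 11 more are added, for 34 in that arm.
- Final rule: "The null hypothesis will be rejected if 18 or more responses are observed in 34 patients on the pamrevlumab arm".
- Claimed properties: "This design yields a type I error rate of 0.05 and power of 90% when the true response rate is 65" percent.

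No other section of the protocol gives a different final boundary.

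**The concern.** Published Simon designs are usually given as two pairs, r1/n1 and r/n. Both r1 and r are the largest counts at which the drug is not taken forward. Section 4.6 uses its Stage 1 number in that sense (9 or fewer may stop the study) but uses 18 as the smallest count for rejection. If 18 is the tabulated r, rejection should start at 19.

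This is the only numerical rejection boundary in the protocol, and the only rule tied to a stated alpha. If the one-sided error of the written rule is well above 0.05, a result of exactly 18 of 34 would be reported as significant at a level it does not reach.

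**Working it through.** **Inputs (all from Protocol section 4.6).** p0 = 0.40, p1 = 0.65, n1 = 23, r1 = 9, n = 34 (23 + 11), final rejection count c = 18. Targets: type I error 0.05 one-sided, power 90%.

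**Formula.** With X1 responses in Stage 1 and X2 in the 11 added patients, the null is rejected if X1 is at least 10 and X1 + X2 is at least c:

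P(reject | p) = Σ over x = 10 to 23 of P(Bin(23, p) = x) × P(Bin(11, p) ≥ c − x)

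The type I error is this sum at p = 0.40, and the power is the sum at p = 0.65.

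**Attempt to reproduce the stated 0.05 and 90%.** Because section 4.6 says only that the study may be stopped, the sum was also run with the futility stop ignored, which reduces it to P(Bin(34, p) ≥ c).

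| Final rule | Type I error, futility binding | Type I error, futility ignored | Power, binding | Power, ignored |
|---|---|---|---|---|
| 18 or more (as written) | 0.0861 | 0.0872 | 0.9471 | 0.9486 |
| 19 or more | 0.0443 | 0.0444 | 0.9002 | 0.9007 |

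Neither stated figure is reproduced at 18. Both targets are met at 19.

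**Hand check by normal approximation, futility ignored.** Under the null the mean is 34 × 0.40 = 13.6 and the SD is √(34 × 0.40 × 0.60) = √8.16 = 2.857.

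- 18 or more, with continuity correction: z = (17.5 − 13.6)/2.857 = 1.365, tail 0.086. Without it: z = (18 − 13.6)/2.857 = 1.540, tail 0.062.
- 19 or more, with continuity correction: z = (18.5 − 13.6)/2.857 = 1.715, tail 0.043.

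A cruder approximation therefore does not yield 0.05 at 18 either.

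**Variants that might rescue the rule.** Keeping 34 patients and rejection at 18, the Stage 1 size was changed to 22 and 24 (with r1 = 9) and r1 to 8, 10 and 11 (with n1 = 23). The lowest type I error was 0.069, at r1 = 11.

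**Which design was intended.** A search over two-stage designs with type I error at most 0.05 and power at least 0.90 found none with a total below 34. At 34, the qualifying design with the smallest expected size under the null is 9/23 with rejection at 19 or more. Its probability of stopping at Stage 1 under the null is 0.556, so its expected size is 23 + (1 − 0.556) × 11 = 27.9. The protocol matches this design in n1, r1 and n, and differs only in the final count, by one.

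**Size of the error.** 0.0861/0.05 = 1.7 times the stated alpha, and 0.0861/0.0443 = 1.9 times the error of the 19 rule. The two rules differ only when exactly 18 of 34 respond. Under the binding rule that outcome has probability 0.0861 − 0.0443 = 0.042 at a true rate of 40%, and 0.9471 − 0.9002 = 0.047 at 65%.

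**The case against.** The strongest objection concerns the role of this test. The trial is randomized 1:1 (section 4.1), the primary endpoint is a proportion (section 3.1), and section 4.7 compares categorical endpoints between arms by Fisher's exact or Cochran-Mantel-Haenszel test. The protocol does not say whether the single-arm Simon test or the between-arm comparison carries the primary inference. That stands as a limit on scope: the inflated error belongs to the test against a fixed 40% rate, not to the randomized comparison. It does not excuse the boundary, because section 4.7 gives no alpha or success threshold for the between-arm tests.

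The two rules also part only at exactly 18 responses, an outcome with a chance of about 4% to 5% at either assumed rate. That is true, but under the null this one outcome nearly doubles the false-positive rate.

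The cause is an inference. The documents show only that the rule and its claimed properties conflict; a slip in reading the tabulated r is the likely explanation, supported by the 90% power, which fits 19 (0.9002) and not 18 (0.947).

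Finally, 0.044 is not unconditional. Section 4.1 allows stopping for efficacy after Stage 1 and gives no boundary. Using that option could only add to the error under either rule.

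The absence of the SAP is no answer: the rule and its claimed error rate are both stated in section 4.6 and disagree there.

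**Conclusion.** The concern holds. The final rule in section 4.6 has an exact one-sided type I error of 0.0861 (0.0872 if the futility stop is not followed) and power of about 95%, against the stated 0.05 and 90%. With the same patient numbers, rejecting at 19 or more gives 0.0443 (0.0444) and 90.0%.

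These figures assume independent responses with a common rate, the null and alternative rates in section 4.6, exactly 23 and 34 evaluable pamrevlumab patients, and no efficacy stop at Stage 1. The correction must be made, because the protocol's only numerical rejection boundary contradicts the alpha stated for it.

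**What to change.** In section 4.6, change the final boundary to 19 or more responses in 34 patients (equivalently, more than 18). State the attained one-sided type I error as 0.044 and the power as 90%, on the condition that there is no efficacy stop at Stage 1.

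If the sponsor prefers to keep 18, the section must instead give the type I error as about 0.086 (0.087 with non-binding futility) and the power as about 95%, and drop the claim of 0.05.

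The cost is one number and one sentence in a protocol amendment. The sample sizes of 23 and 34 and the Stage 1 boundary stay as they are, and no extra patients are needed. The change should be made before the final responder count is known: altering the boundary after exactly 18 responses had been seen would look driven by the data.
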